4.1 Overall Design

Study APC-004 is a randomized, double blind, placebo-controlled, 3-period, single-dose crossover study to evaluate the safety and efficacy of two different dose combinations of AD-109 in patients with mild- to moderate OSA. Participants will undergo initial pre-screening to

determine potential study eligibility. Patients selected for further screening should either have a previous history of OSA of a severity consistent with enrollment criteria or be at high risk (e.g. as assessed by STOP-Bang Questionnaire score). Only patients who meet all non-PSG enrollment criteria at Visit 1 are eligible for a screening PSG.

Patients who meet all enrollment criteria will be randomized to receive the following experimental treatments, one treatment on each of 3 PSG night, separated by at least a one week washout period:

- Atomoxetine 75 mg + R-oxybutynin 2.5 mg (i.e. 75/2.5)
- Atomoxetine 37.5 mg + R-oxybutynin 2.5 mg (i.e. 37.5/2.5)
- Placebo

[figure not shown]
Dosing of the study treatment will occur immediately prior to lights out. The morning following each PSG exam in the crossover period the DSST, KSS, and sleep quality VAS will be administered approximately 1 hour after awakening.

Each PSG night is followed by a 1-week washout period. AE/SAE information is recorded at each study visit and by telephone contact with participants during each washout period.

Primary efficacy and safety endpoints will compare the 75/2.5 and 37.5/2.5 doses to each other and to placebo. AE/SAE information is recorded at each study visit and at the End of Study Evaluation.

Participants who withdraw from the study will not be replaced. No subsequent open-label extension is planned following the study.

Figure 1: Overview of Study Design

PSG = polysomnography.

4.2 Scientific Rationale for Study Design and Dose

Previous Phase 2 studies conducted by Apnimed and academic collaborators support that the combination of atomoxetine and racemic oxybutynin is effective for OSA over a wide range of disease severity. This study will extend findings in patients with mild- to moderate OSA, whereas other planned studies will examine patients with moderate- to severe OSA.

This study is designed to provide additional dose ranging efficacy and safety data for doses of atomoxetine in the middle- and higher-range of doses previously studied. Completed studies of AD036 support efficacy and safety of 5 mg racemic oxybutynin in combination with atomoxetine. Because the R-enantiomer of oxybutynin confers about 2-fold the anticholinergic activity of the racemate, with such activity thought to be the major contributor to efficacy in OSA, the dose of R-oxybutynin will be 2.5 mg in this study.

A detailed description of the chemistry, pharmacology, efficacy, and safety of AD109 is provided in the Investigator's Brochure.

4.3 End of Study Definition

A participant is considered to have completed the study if he/she has completed all phases of the study through the last scheduled procedure shown in the Schedule of Activities (SoA).

The end of the study is defined as the date of the last visit of the last participant in the study or last scheduled procedure shown in the SoA for the last participant in the study globally.

5 Study Population

Eligible participants will be recruited both from the existing clinic population at the study sites, including databases of previous subjects who participated in other studies, and through direct advertising to the community.

Participants must be able to provide written consent and meet all the inclusion criteria and none of the exclusion criteria.

5.1 Inclusion Criteria

Age and Sex

1. Between 25 to 65 years of age, inclusive, at the Screening Visit.

Disease Measures

- 2. AHI 5 to 20 (hypopneas defined by 4% oxygen desaturation)
- 3. PGI-S \geq 1, or history of one or more of the following OSA symptoms:
 - Snoring or nighttime gasping/choking
 - Daytime sleepiness, fatigue, or decreased concentration
 - Nonrefreshing sleep, sleep fragmentation (including from nocturia), or morning headache
 - Irritability, decreased mood or libido

Weight

3. BMI between 18.5 and 40.0 kg/m², inclusive, at the pre-PSG visit.

Male participants:

4. If male and sexually active with female partner(s) of childbearing potential, participant must agree, from Study Day 1 through 1 week after the last dose of study drug, to practice the protocol specified contraception (see Appendix 4: Contraceptive Guidance and Collection of Pregnancy Information).

Female participants:

- 5. If a woman of childbearing potential (WOCBP), the participant must agree, from Study Day 1 through 1 week after the last dose of study drug, to practice the protocol specified contraception (See Appendix 4: Contraceptive Guidance and Collection of Pregnancy Information). All WOCBP must have negative result of a serum pregnancy test performed at screening.
- 6. If female and of non-childbearing potential, the participant must be either postmenopausal (defined as age ≥ 55 years with no menses for 12 or more months without an alternative medical cause) or permanently surgically sterile (bilateral oophorectomy, bilateral salpingectomy or hysterectomy).

Informed Consent

- 7. Participant voluntarily agrees to participate in this study and signs an Institutional Review Board (IRB)-approved informed consent prior to performing any of the Screening Visit procedures.
- 8. Participant must be able to understand the nature of the study and must have the opportunity to have any questions answered.

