1.1 Synopsis

Protocol Title:

Sponsor Study No.:

Phase: 2

Sponsor: Apnimed, Inc.

Rationale:

Apnimed is developing the combination of atomoxetine and oxybutynin for the treatment of obstructive sleep apnea (OSA). Initial Phase 2 studies of the combination were conducted with marketed oxybutynin (combination designated AD-036), which is a racemic mixture of R- and S-oxybutynin. Subsequent development is being pursued with R-oxybutynin (combination designated AD-109), a new enantiomerically pure form of oxybutynin which is proposed to have an improved safety and efficacy profile in OSA compared to racemic oxybutynin.

Previous studies of AD-036 provided dose-response efficacy and safety data across a broad spectrum of OSA disease severity. Study APC-004 is designed to extend and confirm these findings to AD-109 in a population with mild- to moderate OSA, in parallel with other studies of AD-109 planned by Apnimed in moderate- to severe OSA.

Overall Design:

Study APC-004 is a randomized, double blind, placebo-controlled, 3-period, single-dose crossover study in patients with mild- to moderate OSA. A screening visit and polysomnographic (PSG) exam will be conducted to establish that each participant meets study enrollment criteria. Each participant will then receive a single dose of each of the following during 3 overnight PSG exams, each separated by a one week washout period:

- Atomoxetine 75 mg + R-oxybutynin 2.5 mg (i.e. 75/2.5)
- Atomoxetine 37.5 mg + R-oxybutynin 2.5 mg (i.e. 37.5/2.5)
- Placebo

Primary efficacy and safety endpoints will compare the 75/2.5 and 37.5/2.5 doses to each other and to placebo.

Number of Participants:

A total of 30 participants will be enrolled.

Study Duration:

The overall study duration will be up to 12 weeks, as follows:

- Screening, up to 4 weeks;
- 3-period crossover, up to 6 weeks;
- End of Study Evaluation, 2 weeks post crossover period

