1.2 Schedule of Activities (SoA)

Table 1Schedule of Activities

	Screening		3-Way Crossover Period					End of Study Evaluation	
Procedures	V1	V2	V3	Wash-out	V4	Wash-out	V5	Wash-out	Evaluation
Trial Day (Visit Window)	Up to 4 weeks		Up to 6 weeks					2 wks post $V5 \pm 3 d$	
Informed consent	X								
Non-PSG enrollment criteria ²	X								
Demography	X								
Physical exam	X								
Medical history	X								
Clinical laboratory testing	X								X
Pregnancy test ³	X								
12 Lead ECG	X								
PSG Exam		X ⁴	X		X		X		
Randomization ⁵			X						
HS study treatment ⁶			X		X		X		
DSST, KSS, Sleep quality VAS ⁷			X		X		X		
Vital signs ⁸	X	X	X		X		X		
AE/SAE monitoring			X	X	X	X	X	X	X
Prior/concomitant medication	X	X	X	X	X	X	X	X	X

6 January 2021 7 of 54 V2.0

¹ Each washout period is a minimum of 7 days

² Includes ESS, PGI-S, and history of OSA symptoms

³ WOCBP only

⁴ Only patients who meet all non-PSG enrollment criteria at Visit 1 are eligible for a screening PSG

⁵ Randomization occurs when participant meets enrollment criteria up to the time of the first crossover period.

⁶ Study medication administered immediately before lights out

⁷ Administer at similar time after awakening after each crossover PSG, approximately 1 hour after awakening

⁸ Vital signs include the following: seated blood pressure, pulse, respiratory rate; vital signs on PSG nights taken after admission to PSG lab.

Clinical Study Protocol CONFIDENTIAL

Abbreviations: AE = adverse event; DSST = Digit Symbol Substitution Test; ECG = electrocardiogram; ESS = Epworth sleepiness scale; KSS = Karolinska sleepiness scale; PGI-S = patient global impression of severity of OSA; PSG = polysomnography; SAE = serious adverse event; VAS = visual analog scale; WOCBP = women of childbearing potential.

6 January 2021 8 of 54 V2.0

2 Introduction

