Female participants of childbearing potential are eligible to participate if they agree to use a highly effective method of contraception consistently and correctly as described in the table below.

Highly Effective Contraceptive Methods That Are User Dependent¹

Failure rate of <1% per year when used consistently and correctly.

Combined (estrogen- and progestin-containing) hormonal contraception associated with inhibition of ovulation²

- Oral
- Intravaginal
- Transdermal

Progestogen-only hormonal contraception associated with inhibition of ovulation

- Oral
- Injectable

Highly Effective Contraceptive Methods That Are User Independent¹

Implantable progestogen-only hormonal contraception associated with inhibition of ovulation

- IUD
- Intrauterine hormone-releasing system (IUS)
- Bilateral tubal occlusion

Vasectomized partner

A vasectomized partner is a highly effective contraception method provided that the partner is the sole male sexual partner of the WOCBP and the absence of sperm has been confirmed. If not, an additional highly effective method of contraception should be used.

Sexual abstinence

Sexual abstinence is considered a highly effective method only if defined as refraining from heterosexual intercourse during the entire period of risk associated with the study treatment. The reliability of sexual abstinence needs to be evaluated in relation to the duration of the study and the preferred and usual lifestyle of the participant.

NOTES:

1 Typical use failure rates may differ from those when used consistently and correctly. Use should be consistent with local regulations regarding the use of contraceptive methods for participants participating in clinical studies.

Pregnancy Testing

- WOCBP should only be included after a confirmed menstrual period and a negative highly sensitive serum pregnancy test.
- An additional serum pregnancy testing should be performed at Visit 5 (EOS).

• Pregnancy testing will be performed whenever a menstrual cycle is missed or when pregnancy is otherwise suspected.

Collection of Pregnancy Information:

Female participants who become pregnant

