- The Investigator will collect pregnancy information on any female participant who becomes pregnant while participating in this study. Information will be recorded on the appropriate form and submitted to the Sponsor within 24 hours of learning of a participant's pregnancy. The participant will be followed to determine the outcome of the pregnancy. The Investigator will collect any follow up information on the participant and the neonate and the information will be forwarded to the Sponsor. Generally, follow up will not be required for longer than 6 to 8 weeks beyond the estimated delivery date. Any termination of the pregnancy will be reported, regardless of fetal state (presence or absence of anomalies) or indication for the procedure.
- While pregnancy itself is not considered to be an AE or SAE, any pregnancy complication or elective termination of a pregnancy will be reported as an AE or SAE. A spontaneous abortion is always considered to be an SAE and will be reported as such. Any post-study pregnancy-related SAE considered reasonably related to the study treatment by the Investigator will be reported to the Sponsor. While the Investigator is not obligated to actively seek this information in former study participants, he or she may learn of an SAE through spontaneous reporting.
- Any female participant who becomes pregnant while participating in the study will be withdrawn from the study.

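### No scheduled pregnancy check falls close to the first dose: the only pre-dose test is at V1, up to 28 days earlier, and contraception is mandated only from Study Day 1

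*Protocol*

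**What the plan says.** **Testing.** Protocol 5.1, inclusion 5: "All WOCBP must have negative result of a serum pregnancy test performed at screening". The SoA (Protocol 1.2, repeated in SAP Appendix A) marks one pregnancy test, at V1. Protocol 9.2 (Appendix 2) allows further testing of WOCBP at need. Protocol 9.4 (Appendix 4) makes inclusion conditional on a confirmed menstrual period as well as the negative serum test, and adds: "Pregnancy testing will be performed whenever a menstrual cycle is missed or when pregnancy is otherwise suspected". It also calls for a second serum test at Visit 5, which it labels end of study.

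**Timing.** The synopsis gives "Screening, up to 4 weeks". The first dose is at V3. SoA footnote 5 reads "Randomization occurs when participant meets enrollment criteria up to the time of the first crossover period", and the randomization row is marked at V3. Footnote 1 reads "Each washout period is a minimum of 7 days".

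**Contraception.** Inclusion 5 also requires that "the participant must agree, from Study Day 1 through 1 week after the last dose of study drug, to practice the protocol specified contraception". The protocol does not define Study Day 1. SAP 4.6 counts study days so that day 1 is the date of randomization. Protocol 6.4 lists hormonal contraceptives among the medications generally allowed if stable for 1 month before enrollment.

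**Consequence of pregnancy.** Exclusion 12 bars pregnant or nursing women. Appendix 4 states: "Any female participant who becomes pregnant while participating in the study will be withdrawn from the study".

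**The concern.** Exclusion 12 applies up to the first crossover period, yet no scheduled step would reveal a pregnancy begun after V1. The V1 result can be four weeks old, and the dated contraception duty does not cover screening. Appendix 4's missed-cycle rule is a real safeguard, but it is reactive: a woman who conceived shortly before V3 has not yet missed a period. No SoA row asks about menses, and the contact between visits is specified for another purpose: "AE/SAE information is recorded at each study visit and by telephone contact with participants during each washout period".

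At stake is participant safety. A woman whom the protocol excludes, and would withdraw once her pregnancy was known, could be dosed with every scheduled procedure followed. Nothing in the efficacy analysis is affected.

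**Working it through.** **1. The plan's own interval.** Screening of 4 weeks × 7 = 28 days. The stated parts add up: 4 + 6 + 2 = 12 weeks, the stated overall duration. So V1 to V3 can be up to 28 days.

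**2. When the contraception duty starts.** If Study Day 1 is the randomization date and randomization is at V3, no dated duty covers V1 to V3. If randomization comes earlier, it still cannot precede V2, because the AHI criterion needs the screening PSG done there. V1 to V2 is therefore undated on either reading.

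**3. Window when missed-cycle testing works.** Let D be the days from V1 to V3 and M the days from conception to missed menses. The documents do not give M; assume 14, range 10 to 18. A conception after V1 and fewer than M days before V3 triggers no test before the first dose, so the window is min(D, M).

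| D (days) | M (days) | Window (days) |
|---|---|---|
| 7 | 14 | 7 |
| 14, 21 or 28 | 14 | 14 |
| 28 | 10 to 18 | 10 to 18 |

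This counts conceptions after V1 only. Conceptions just before V1 that the V1 test cannot yet see would lengthen the D = 7 row but leave the D = 28 row unchanged.

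**4. Effect of the confirmed menses.** Assume a regular 28-day cycle with ovulation on day 14. If the confirmed menses began k days before V3 (k up to 28), the window is max(0, k − 14): 0 days for k of 14 or less, 7 for k = 21, 14 for k = 28. Hence about 0 to 14 days. Appendix 4 sets no limit on k.

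**5. Study doses before detection (M = 14, minimum washouts).** V4 is at day 7 or later after V3, and V5 at day 14 or later. For a conception c days before V3, the missed period falls on day 14 − c.
- 7 < c < 14: before day 7, so one dose.
- 0 < c < 7: between days 7 and 14, so up to two doses, and before V5.

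SAP 3.2.1 uses six balanced sequences, with placebo first in two of them. One dose is active with probability 4/6 = 0.67; two doses average 2 × 2/3 = 1.33 active. The count depends on M: at M = 18, a conception in the last 4 days before V3 could put the missed period after day 14. Even then no one receives more than two active doses, because each participant's three doses include placebo.

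**6. What each remedy gains.** Let L be the hCG detection lag, assumed 7 to 14 days.
- V3 test, missed-cycle rule working (M = 14): the window falls from 14 to min(14, L) = 7 to 14 days, a gain of 0 to 7 days.
- V3 test, rule not triggered (irregular cycles or unreported missed cycle): the window is D + L = 28 + 7 to 28 + 14 = 35 to 42 days without the test, and L = 7 to 14 days with it.
- Contraception from V1: required cover extends back by up to 28 days, including the last 7 to 14 days that a V3 test cannot see.

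**The case against.** The strongest reply is that the protocol already has several overlapping safeguards. The confirmed menstrual period, if recent, closes the window entirely. Testing is triggered by any suspicion of pregnancy as well as by a missed cycle, and Appendix 2 leaves room for more. Under the 1-month stability rule, established users of hormonal contraception would normally be covered during screening. The other accepted methods (IUD, tubal occlusion, a vasectomized partner, habitual abstinence) are typically in place before Day 1. Study Day 1 is being read from a SAP derivation that was not written to date a contraception duty. The documents describe no reproductive harm from one or two single doses, and a V3 test gains little where missed-cycle testing works.

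Most of this stands, and it limits the size of the point. Exposure falls mainly on women who start a method only at Day 1. But the menses condition has no date and no SoA entry, discretionary testing requires nothing, and the stability rule governs permitted medication without imposing contraception. Together they make a missed pregnancy less likely; they do not ensure a check before dosing.

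A reader might infer a fixed 14-day gap. The documents contain no such figure; 14 days is the upper end for a regular 28-day cycle under stated assumptions. Nor do they support reading the plan as permitting dosing in pregnancy: exclusion 12 remains in force, and what is missing is a scheduled means of applying it.

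**Conclusion.** The point holds as a minor safety improvement. The documents establish that the only scheduled pre-dose test is at V1, that it can be up to 28 days old at V3, that contraception is not mandated from V1, and that no check is required before the first dose.

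The uncovered window depends on assumed physiology: about 0 to 14 days for a regular 28-day cycle, 10 to 18 days if the conception-to-missed-menses interval varies and V1 to V3 is 28 days, and longer only if cycles are irregular or a missed cycle goes unreported. At the 14-day assumption an affected woman could receive one or two study doses, one of which may be placebo. The number of WOCBP among the 30 is not given, and the absolute risk is small.

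The end-of-study test is a separate inconsistency. V5 is the third dosing night, the End of Study Evaluation is 2 weeks later, and the SoA marks the test at neither. Protocol section 7 makes adherence to the SoA mandatory, so a site following it would omit the test. A reader might take this as further evidence of the pre-dose gap. It is not, because that test comes after first dosing.

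**What to change.** 1. Start the contraception requirement in inclusion 5 at V1 (screening) instead of Study Day 1. This is the more useful change, since it covers the recent conceptions that no test at V3 would detect.
2. Add to the SoA a urine hCG for WOCBP at V3, negative before randomization and dosing, in addition to the V1 serum test. Urine suits because the SoA has no blood draw at V3 and the result is needed that evening. Record the date of last menses at V1 and V3. The V3 test alone gains only about 0 to 7 days if missed-cycle testing works; its larger value is where that rule fails.
3. Separately, mark Appendix 4's second serum test in the SoA at the End of Study Evaluation and correct the Visit 5 label.

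Cost: one protocol amendment with IRB approval, one urine test per WOCBP, and one serum hCG per WOCBP on the existing end-of-study draw. If 3 to 10 of the 30 are WOCBP (an assumption), that is 3 to 10 of each. No new visit or staff is needed.

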5.2 Exclusion Criteria

Participants are excluded from the study if any of the following criteria apply:

Medical Conditions

- 1. History of narcolepsy.
- 2. Clinically significant craniofacial malformation.
- 3. Clinically significant cardiac disease (e.g., rhythm disturbances, coronary artery disease or cardiac failure) or hypertension requiring more than 2 medications for control (combination medications are considered as 1 medication for this purpose).
- 4. Clinically significant neurological disorder, including epilepsy/convulsions.
- 5. History of schizophrenia, schizoaffective disorder or bipolar disorder according to Diagnostic and Statistical Manual of Mental Disorders-5 (DSM-5) or International Classification of Disease tenth edition criteria.
- 6. History of attempted suicide or suicidal ideation within 1 year prior to screening, or current suicidal ideation.
- 7. History of clinically significant constipation, gastric retention, urinary retention or insomnia.
- 8. Medically unexplained positive screen for drugs of abuse (excluding THC/marijuana) or history of substance use disorder as defined in DSM-V within 24 months prior to Screening Visit.
- 9. A significant illness or infection requiring medical treatment in the past 30 days.
- 10. Clinically significant cognitive dysfunction as determined by investigator.
- 11. Untreated narrow angle glaucoma.
- 12. Women who are pregnant or nursing.

Prior/Concomitant Therapy

- 13. CPAP should not be used for at least 2 weeks prior to first study PSG and throughout the study.
- 14. History of using oral or nasal devices for the treatment of OSA may enroll as long as the devices are not used during participation in the study.

- 15. History of using devices to affect participant sleeping position for the treatment of OSA, e.g. to discourage supine sleeping position, may enroll as long as the devices are not used during participation in the study.
- 16. History of oxygen therapy.
- 17. Use of medications from the list of disallowed concomitant medications.
- 18. Treatment with strong cytochrome P450 3A4 (CYP3A4) inhibitors, strong cytochrome P450 2D6 (CYP2D6) inhibitors, or monoamine oxidase inhibitors (MAOI) within 14 days of the start of treatment, or concomitant with treatment.

Prior/Concurrent Clinical Study Experience

19. Use of another investigational agent within 30 days or 5 half-lives, whichever is longer, prior to dosing.

Diagnostic Assessments

20. Hepatic transaminases >2X the upper limit of normal (ULN), total bilirubin >1.5X ULN (unless confirmed Gilbert syndrome), estimated glomerular filtration rate < 60 ml/min.

Other Exclusions

- 21. <5 hours typical sleep duration.
- 22. ESS > 18
- 23. Night- or shift-work sleep schedule which causes the major sleep period to be during the day.
- 24. Employment as a commercial driver or operator of heavy or hazardous equipment.
- 25. Smoking more than 10 cigarettes or 2 cigars per day, or inability to abstain from smoking during overnight PSG visits.
- 26. Unwilling to use specified contraception.
- 27. Unwilling to limit during the study period alcohol consumption to no greater than 2 units/day for men or 1 unit/day for women, not to be consumed within 3 hours of bedtime.
- 28. Unwilling to limit during the study period caffeinated beverage intake (e.g., coffee, cola, tea) to 400 mg/day or less of caffeine, not to be used within 3 hours of bedtime.

- 29. Any condition that in the investigator's opinion would present an unreasonable risk to the participant, or which would interfere with their participation in the study or confound study interpretation.
- 30. Participant considered by the investigator, for any reason, an unsuitable candidate to receive AD109 or unable or unlikely to understand or comply with the dosing schedule or study evaluations.

